#### Rationale:

Although effective drug treatment exists for asthma, many people continue to have distressing symptoms and impaired quality of life. Recent surveys show that over half of all adults with asthma in the UK are not properly controlled on their current treatment regimen, resulting in impaired quality of life, and increased costs to the community.

Many people with asthma are interested in non-drug asthma treatments, particularly in breathing exercises. Several recent studies have shown benefits from undergoing a short breathing exercises course taught by a respiratory physiotherapist for people who remained symptomatic despite usual treatment. There is currently not enough access to suitable trained

physiotherapists to provide such a service to most people with asthma in the UK. We propose to provide the same breathing retraining programme we have previously shown to be effective when taught 'face-to-face' by a physiotherapist or as a DVD, that patients can use in their own home in addition to their standard treatment. We will see whether this type of instruction is better than the 'usual care' that is currently provided, and whether it is as good as the 'face-to-face' physiotherapist instruction (which is more expensive and less convenient for patients).

We hypothesise that breathing retraining exercises taught by an audio-visual educational package consisting of a instructional DVD programme and supporting written information will result in clinically important improvements in asthma-related quality of life and in asthma control above 'usual care' and of a similar magnitude to those resulting from 'face-to-face' physiotherapist instruction.

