#### 1. For equivalence of DVD programme and face-to-face programme.

In a previous HTA study comparing different pharmacotherapy options in asthma (the ELEVATE study, Controlled-Trials.com number, ISRCTN99132811, Price et al, 2011), treatments were deemed to be equivalent if the 95% CI for mean difference between groups in AQLQ was wholly included between -0.3 and +0.3. Our sample size calculation for equivalence therefore uses the same equivalence boundary (i.e. between -0.3 and +0.3). However, we have assumed that the SD of the between group difference in AQLQ will be a conservative 25% smaller (i.e. 0.77) than that reported in our GLAD study (1.03). The justification for this is that the proposed equivalence analysis will compare two breathing training interventions as opposed to a breathing intervention versus usual care in the GLAD study. Since this is an equivalence study, as opposed to a non-inferiority study, a two-tailed 5% significance level was used in the calculations (29). Following published guidelines (30), the equivalence margin was therefore selected to be 'the largest difference that can be judged to be clinically acceptable and should be smaller than differences observed in superiority trials of the active comparator'.

Using Nquery 7.0 (specifically the MTEOU-1 two group t-test of equivalence in means – unequal n's program), the following justification of the sample size is obtained:

Sample sizes of 210 in the DVD breathing retraining group and 105 in the 'face-to-face' physiotherapy group are required to assess treatment equivalence with 90% power using an equivalence boundary for AQLQ of 0.3. This assumes: that the expected between group difference in mean AQLQ is zero; a two tailed 5% significance level; common standard deviation for AQLQ of 0.77 and a lower/upper limit of -0.3/+0.3 for the 95% confidence interval of the between group difference in AQLQ.

In the unlikely event that the between group AQLQ standard deviation is higher than our estimated 0.77, assuming all other parameters stayed the same, we would still have 80% power to declare equivalence between the DVD breathing retraining group and the 'face-to-face' physiotherapy group as long as the between group SD was no higher than 0.89.

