#### Statistical Analysis:

#### 1. Analysis plan for equivalence study

Analysis and reporting of the equivalence comparison will follow published guidelines. It is known that full analysis set or ITT may lead to bias (from protocol violators, withdrawals and dropouts) and a resultant increase in type 1 error risk. Therefore, for the equivalence study, an ITT and a per protocol analysis will run simultaneously, neither having supremacy over the other. They should hopefully lead to similar conclusions giving the study a robust interpretation.

A 95% CI will be constructed for the mean difference in 12 month total AQLQ score between the DVD arm and the 'face-to-face' breathing retraining arm. Since the equivalence boundary is set at 0.3, equivalence will be declared if the 95% CI is wholly included between -0.3 and +0.3. If equality is not evident, then ANCOVA will be used to examine whether the 'face-to-face' breathing retraining arm is superior to the DVD arm via examination of the difference (and 95% confidence interval) of 12 month total AQLQ score (and each of the four domain scores) before and after adjustment for baseline AQLQ score and potential covariates such as age, gender, practice, smoking status etc.

BREATHE Page 27 of 35 Protocol v6 01-08-2014

ANCOVA will also be used to analyse the difference (and 95% confidence interval) for the secondary outcome measures (ACQ, lung function, fraction of exhaled nitric oxide, EuroQOL, anxiety and depression score, hyperventilation and patient enablement scores) at 12 months before and after adjustment for baseline values and potential confounders. Since we have data on AQLQ, ACQ and HADS at four time points (baseline, 3, 6 and 12 months) a repeated measures analysis will be used to examine change in each of these outcomes over time. For those secondary outcomes which involve count data (i.e. oral corticosteroid courses, bronchodilator use, asthma related healthcare resource use), Poisson regression analyses with a log link function will be performed to give rate ratios (and their 95% confidence intervals) in the DVD and 'face-to-face' breathing retraining arm both before and after adjustment for potential confounders such as smoking status and sociodemographic factors.

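### The DVD versus face-to-face analysis defines no conclusion for a DVD that is non-inferior or better, although the rationale and the cost-minimisation trigger need one

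*Protocol*

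**What the plan says.** Section 8.1, analysis plan for the equivalence study, sets up a 95% CI for the difference in 12-month total AQLQ between the DVD and face-to-face arms, and states that "equivalence will be declared if the 95% CI is wholly included between -0.3 and +0.3". If this is not met, "ANCOVA will be used to examine whether the 'face-to-face' breathing retraining arm is superior to the DVD arm", using the difference and its 95% CI before and after adjustment. No other conclusion is named, and the direction of the difference is not fixed. ITT and per-protocol analyses run side by side, with neither taking precedence.

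Three other places bear on this rule:

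- **Section 8.1, sample size for equivalence.** The choice is explicit: "Since this is an equivalence study, as opposed to a non-inferiority study", and so "a two-tailed 5% significance level was used in the calculations".
- **Trial Synopsis, Rationale.** The trial is to see "whether it is as good as the 'face-to-face' physiotherapist instruction (which is more expensive and less convenient for patients". The next paragraph hypothesises an effect comparable in size to that of face-to-face instruction.
- **Section 7, Health economic evaluation.** A cost-minimisation analysis of the two programmes is to follow if non-inferiority between them has been proven. The protocol defines no non-inferiority test.

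**The concern.** The equivalence rule is two-sided, while two parts of the protocol need a one-sided answer. Take a 95% CI for DVD minus face-to-face of +0.02 to +0.38. It excludes any loss from using the DVD, but its upper limit exceeds +0.3, so equivalence is not declared. The plan then turns only to face-to-face superiority, which this interval already excludes. A milder case is -0.04 to +0.32: a loss of 0.3 or more is excluded, yet the protocol has no name for that result.

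Two things are at stake. A non-inferiority claim made after the data are seen, however well the interval supports it, is open to challenge as post hoc. And the economic analysis has a trigger that the statistical section never produces, so whether cost minimisation is run would be settled after the results are known.

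**Working it through.** **Inputs** (protocol, Section 8.1): 210 DVD and 105 face-to-face analysed; "common standard deviation for AQLQ of 0.77"; margin 0.3; two-sided 95% CI; planned true difference 0. For sensitivity, the protocol gives an SD of 0.89 as the limit for 80% power, and 1.03 from the earlier face-to-face trial. Two assumptions are mine: the difference *d* is DVD minus face-to-face with higher AQLQ better, and *d* = 0.10 serves as an illustration.

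**Formulae** (normal approximation):

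- SE = SD × √(1/210 + 1/105)
- P(equivalence) = Φ((0.3 − d)/SE − 1.96) − Φ((−0.3 − d)/SE + 1.96)
- P(lower limit above −0.3) = Φ((0.3 + d)/SE − 1.96)

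**The plan's own figures first.** The protocol states 90% power at SD 0.77 and 80% at SD 0.89.

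- SD 0.77: SE = 0.77 × 0.1195 = 0.0920, and 0.3/0.0920 − 1.96 = 1.30. The lower limit clears −0.3 with probability Φ(1.30) = 90.3%. Both limits lie inside ±0.3 with probability 2 × 0.903 − 1 = 80.6% (80.3% with the t distribution).
- SD 0.89: SE = 0.1064. The same two probabilities are 80.5% and 61.0%.
- A 90% CI rule (5% on each side) would give 89.4% and 76.0%.

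Both stated powers therefore match the one-sided reading at 2.5%, and not the 95% CI equivalence rule. That mismatch is a separate matter. What counts here is that the planned numbers already support a non-inferiority reading.

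**If the DVD is better by 0.10 (SD 0.77).**

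- P(equivalence) = Φ(0.2/0.0920 − 1.96) − Φ(−0.4/0.0920 + 1.96) = Φ(0.21) − Φ(−2.39) = 57.6%.
- P(lower limit above −0.3) = Φ(0.4/0.0920 − 1.96) = Φ(2.39) = 99.1%.

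| SD | True difference | Equivalence rule met | Lower limit above −0.3 | Non-inferior but not equivalent |
|---|---|---|---|---|
| 0.77 | 0 | 80.6% | 90.3% | 9.7% |
| 0.77 | +0.10 | 57.6% | 99.1% | 41.6% |
| 1.03 | 0 | 36.7% | 68.3% | 31.7% |
| 1.03 | +0.10 | 27.0% | 90.1% | 63.1% |

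**Where the gap lies.** At SD 0.77 the half-width is 1.96 × 0.0920 = 0.18, and 0.30 − 0.18 = 0.12. By observed difference:

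| Observed DVD minus face-to-face | What the interval shows | Conclusion in the plan |
|---|---|---|
| below −0.18 | face-to-face superior | yes, by the fallback |
| −0.18 to −0.12 | neither | equivalence not declared, face-to-face superiority not shown |
| −0.12 to +0.12 | equivalence | yes |
| +0.12 to +0.18 | non-inferiority only | none named |
| above +0.18 | non-inferiority and DVD superiority | none named |

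The last two rows are the gap. A two-directional superiority test alone would close only the last.

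**The case against.** Equivalence is a deliberate choice, made in Sections 1.1, 3 and 8.1, and it fits the hypothesis of a comparable effect in the synopsis. Choosing it over non-inferiority is not an error. This stands, and the point does not ask for another design.

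A reader might infer that the plan treats a better DVD as a failure, or that it cannot answer its own question. The documents do not support either reading. An interval inside ±0.3 does answer the question. When equivalence is not shown, the two-sided interval is still reported and would show a DVD advantage as plainly as a deficit. The protocol says only when equivalence is declared and nowhere calls the alternative a failure. The DVD also has its own superiority comparison with usual care. What is missing is a pre-specified conclusion, not the information.

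The size also needs care. The protocol plans on a true difference of 0 and describes the evidence as strongest for face-to-face delivery, so a DVD advantage of 0.10 is only illustrative. The SD 1.03 rows mainly reflect the SD assumption. Non-inferiority is the weaker claim, so its higher probability is expected and is not power that the equivalence test has lost.

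Finally, a list of readings for each position of the interval often sits in the SAP, which is not at hand. That would excuse silence. But the protocol itself fixes the rule, a one-directional fallback and an economic trigger, and these three do not fit together.

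**Conclusion.** The point holds as a gap and an internal inconsistency. Section 8.1 names equivalence and, failing that, face-to-face superiority. It leaves a non-inferior or better DVD without a conclusion, although the Rationale asks for one and the cost-minimisation trigger in Section 7 requires one.

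Under the protocol's planning values (210 and 105, SD 0.77, true difference 0), about 10% of trials would show non-inferiority without equivalence (90.3% − 80.6%). If the DVD were better by 0.10, about 42% would. These figures assume normality, a common SD and the unadjusted interval.

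It would go too far to call a DVD with a lower limit above −0.3 no worse than face-to-face. An interval of −0.29 to +0.07 meets that condition, and the equivalence rule too, while leaving a loss just under 0.3 possible. The supportable label is non-inferior within the 0.3 margin.

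**What to change.** Keep equivalence, the two-sided 95% CI and the 0.3 margin. In the equivalence analysis plan of Section 8.1, define the difference as DVD minus face-to-face and pre-specify, for both the ITT and the per-protocol analysis:

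1. Lower limit above −0.3: the DVD is non-inferior within the 0.3 margin.
2. Upper limit also below +0.3: the two programmes are equivalent.
3. If equivalence is not shown: examine superiority in either direction.

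State which interval carries each conclusion, since the present fallback is ANCOVA before and after adjustment, and what is concluded if the ITT and per-protocol results disagree. In Section 7, tie cost minimisation to one of these named conclusions. In the sample-size section, reconcile the statement that sets equivalence against non-inferiority.

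The cost is a few sentences. Conclusion 1 is one of the two one-sided 2.5% tests already inside the equivalence rule, so it spends no extra alpha. At SD 0.77 it needs 208 and 104 analysed for 90% power, and 210 and 105 are planned. The downside is that the headline may be non-inferiority, a weaker claim than equivalence. The text should be settled before the data are unblinded.

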#### 2. Analysis plan for superiority study

Baseline comparability between the three arms of the trial will be evaluated by examination of summary statistics (the mean and standard deviation or median and interquartile range for continuous variables, dependent on their distribution, and the number and percentage for categorical variables). In accordance with CONSORT guidelines, all comparative analysis will be conducted on an intention to treat (ITT) basis with a per protocol analysis performed as a sensitivity analysis.

For the primary outcome, analysis of covariance (ANCOVA) will be used to examine the 12-month total AQLQ score (and each of the four domain scores) across the three arms with initial adjustment for baseline AQLQ score and then for other potential covariates such as age, gender, practice, smoking status etc. Pair wise comparisons of AQLQ differences will be examined between the 'usual care' arm and each of the DVD and 'face-to-face' breathing retraining arms via calculation of one sided 95% confidence intervals. If the confidence interval includes +0.3 then superiority of either the DVD or 'face-to-face' breathing retraining arms over usual care will be rejected.

In a similar way, ANCOVA will also be used to analyse the continuous secondary outcome measures (ACQ, lung function, fraction of exhaled nitric oxide, EuroQOL, anxiety and depression score, hyperventilation and patient enablement scores). Since we have data on AQLQ, ACQ and HADS at four time points (baseline, 3, 6 and 12 months) a repeated measures analysis will be used to examine change in each of these outcomes over time. The 'usual care' arm will be compared to each of the DVD and 'face-to-face' breathing retraining arms in turn.

For those secondary outcomes which involve count data (i.e. oral corticosteroid courses, bronchodilator use, asthma related healthcare resource use), Poisson regression analyses with a log link function will be performed to give rate ratios in the DVD and 'face-to-face' breathing retraining arm compared to 'usual care' both before and after adjustment for potential confounders such as smoking status and sociodemographic factors.

BREATHE Page 28 of 35 Protocol v6 01-08-2014

Data and all appropriate documentation will be stored for a minimum of 5 years after the completion of the trial, including the follow-up period.

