#### 4. SELECTION AND ENROLEMENT OF SUBJECTS

#### 4.1 SCREENING AND PRE-REGISTRATION / RANDOMISATION EVALUATIONS

We plan to recruit 585 patients (234 in each of the DVD and 'usual care' arms and 117 in the 'face-to-face' physiotherapy arm) from 20 general practice centres, aiming for up to 30 subjects per GP centre. All general practices now have 'asthma registers' of all patients with currently active asthma, as this is a requirement for payment under the NHS Quality and Outcomes Framework system. Patients on the practice asthma register meeting the inclusion criteria below and who have received prescriptions for any asthma medication in the previous 12 months will be identified from the practice computer records by practice staff. A mail merge will be performed at the practice sending out a study invitation letter with full information. People wishing to have more information about the trial will be provided with contact telephone numbers to enable them to speak to study staff at the University of Southampton Clinical Trials Unit (UoSCTU), or encouraged to talk to their GP. People potentially interested in study participation will be asked to provide contact details, to complete the mini-AQLQ (Asthma Quality of Life Questionnaire (23) and to

BREATHE Page 17 of 35 Protocol v6 01-08-2014

return these to the Study Co-ordinator in a pre-addressed stamped envelope. Only those with impaired health status (AQLQ score <5.5) will be recruited, as lack of impairment in health status does not allow 'room for improvement' in the primary outcome measure. In our previous work and other studies, 75% or more or people with asthma treated in the community have impaired health status.

Subjects meeting the entry criteria will be given an appointment to see the study nurse for the baseline visit, which will occur at the subject's general practice at a mutually convenient time. Any questions about the study will be answered, and informed consent obtained. A study nurse will perform the baseline assessment. This will consist of:

- Facilitating subject completion of validated questionnaires: Disease-specific health status (AQLQ) (23), Nijmegen hyperventilation questionnaire (24), Generic health status (EuroQOL, EQ-5D) (25); anxiety and depression scores (HAD questionnaire) (26), Asthma control questionnaire (ACQ) (27).
- Clinical details: Smoking status, asthma history, co-morbidities, medication, and exacerbation frequency.

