- Physiological measurements: Spirometry (FEV1, FEV1/FVC ratio, PEFR), measured with standardized calibrated portable spirometer; Fraction of exhaled nitric oxide (FENO), measured with Aerocrine Mino portable monitor.

If a clinical assessment of potentially dangerous or unstable asthma is made by the trained study nurse, the subject will not enter the study but will be referred urgently back to their usual primary care asthma clinician. Participants who score greater than or equal to 16 in the HADs Questionnaire will be sent a letter from the trial team advising that they may wish to discuss this with their GP. When informed consent has been provided and the baseline assessment completed, the study nurse will telephone UoSCTU for randomisation (or use the web based system when in place). Those randomised to 'usual care' will be informed that they will be posted questionnaires in 3 and 6 months' time to complete and return to the study co-ordinator, and that a final assessment visit will be scheduled for 12 months post randomisation. Contact information will be provided. Those randomised to the DVD intervention will be provided with the written instructional material developed in phase 1 and the DVD. For those who do not have a DVD player at home, an inexpensive DVD player will be provided; it is however anticipated that most people will have access to one of these media players. Subjects will be given information that they will be posted questionnaires in 3 and 6 months to complete and return to the coordinator, and that a final assessment visit will be scheduled for 12 months. Contact information will be provided. For those randomised to the 'face-to-face' physiotherapy arm, they will be informed that they will receive 3 short sessions of contact with a respiratory physiotherapist for breathing retraining. These sessions will be approximately 30-40 minutes long and will occur at roughly 2 weekly intervals following randomisation. The retraining can occur at either the GP surgery, clinic setting or the patient's home according to convenience and preference. The content of the retraining programme

BREATHE Page 18 of 35 Protocol v6 01-08-2014

will be based on those shown to be effective in recent studies (16-18), and similar to the content of the DVD intervention.

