#### **APPENDICES**

# APPENDIX 1 TRIAL OVERSIGHT – Communication and Relationship between Parties

#### APPENDIX 2 BREATHE STUDY FLOW DIAGRAM

- 1. Identification of potential subjects in participating practices:
- Age 16-70yrs
- On asthma register
- Receipt of at least 1 prescription for asthma medication in the previous 12 months

- 2. Mailed invitation to participate in study
- Study information and contact number
- Mini-AQLQ questionnaire to complete and return

- 3. Baseline assessment (at GP surgery), informed consent, randomisation
- Physiological measurements
- Questionnaire completion
- Randomisation to groups 1,2 and 3 (blinded to observer)

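### Two mini-AQLQ scores are taken before randomisation, but the primary ANCOVA names only one: a small, cheap loss of precision, not a bias

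*Protocol*

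**What the plan says.** Protocol section 4.1 asks people interested in the trial "to complete the mini-AQLQ (Asthma Quality of Life Questionnaire (23) and to" return it to the study co-ordinator, and the Appendix 2 flow diagram lists the same step with the mailed invitation ("Mini-AQLQ questionnaire to complete and return"). That score decides entry: "Only those with impaired health status (AQLQ score <5.5) will be recruited". Those who qualify are then given a baseline appointment, where the nurse's assessment includes "Facilitating subject completion of validated questionnaires: Disease-specific health status (AQLQ) (23"), citing the same instrument reference. Randomisation comes afterwards: "When informed consent has been provided and the baseline assessment completed, the study nurse will telephone UoSCTU for randomisation". The schedule of observations agrees, with the questionnaire at pre-screen and again at baseline.

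For the primary outcome, section 8.1 (analysis plan for superiority) fits an ANCOVA to the 12-month AQLQ "with initial adjustment for baseline AQLQ score and then for other potential covariates such as age, gender, practice, smoking status etc". The same section counts AQLQ data at four occasions only: "Since we have data on AQLQ, ACQ and HADS at four time points (baseline, 3, 6 and 12 months"). The postal score is not among them.

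The analysis plan for equivalence describes a 95% confidence interval for the DVD versus face-to-face difference in 12-month total AQLQ, and does not say that this interval is adjusted for anything. Baseline adjustment appears only in the ANCOVA that follows if equivalence is not shown.

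**The concern.** A single questionnaire score is a noisy reading of a patient's usual level. A second reading of the same instrument, also taken before randomisation, can remove part of that noise from the 12-month comparison. Because the postal score is an entry condition, it should exist for everyone enrolled, and because it precedes randomisation, adjusting for it cannot introduce bias. The protocol uses it for eligibility and names no further use. At stake is the width of the intervals for the AQLQ comparisons, which are judged against a boundary of 0.3.

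**Working it through.** **The plan's own figures.** The stated 92% power for face-to-face against usual care uses 105 and 210 patients, a difference of 0.38, SD 1.03 and a one-sided 5% test. The standard error is 1.03 × √(1/105 + 1/210) = 0.1231, the noncentrality 0.38/0.1231 = 3.09, and the noncentral t gives 92.4%. It reproduces. Recruitment also reproduces: 210/0.9 = 234 twice, plus 105/0.9 = 117, makes 585. Neither calculation takes credit for baseline adjustment, so the omission makes neither wrong.

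**Inputs for the gain.** Let p be the correlation of postal with visit score, b that of visit with 12-month score, and s that of postal with 12-month score. The protocol gives none of them. Assumed: p 0.7 to 0.9; b and s 0.5 to 0.7; s not above b, because the postal score is earlier and completed without the nurse. For the truncation, section 4.1 says: "In our previous work and other studies, 75% or more or people with asthma treated in the community have impaired health status". I take 75% below 5.5, the cut applied to the postal score only, and normal scores scaled to unit variance.

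**Formulas.**
- Variance of the postal score after truncation: with c = 0.6745 (75th percentile) and λ = φ(c)/0.75 = 0.4237, it is 1 − cλ − λ² = 0.535. Write h = 1 − 0.535 = 0.465.
- Residual variance of the 12-month score given both scores, unchanged by selecting on the postal score: V2 = 1 − (b² + s² − 2pbs)/(1 − p²).
- Residual variance given the visit score alone, after truncation: V1 = (1 − s²h) − (b − psh)²/(1 − p²h).
- Variance cut = 1 − V2/V1. Interval narrowing = 1 − √(V2/V1).

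**Worked mid-range case** (p = 0.8, b = s = 0.6):
- V2 = 1 − 0.144/0.36 = 0.600.
- V1 = 0.8325 − 0.3767²/0.7022 = 0.6305.
- Variance cut = 1 − 0.600/0.6305 = 4.8%; narrowing 2.4%.

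**Range.**

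| p | b | s | V1 | V2 | Variance cut | Narrowing |
|---|---|---|---|---|---|---|
| 0.7 | 0.7 | 0.7 | 0.4834 | 0.4235 | 12.4% | 6.4% |
| 0.8 | 0.7 | 0.7 | 0.4970 | 0.4556 | 8.3% | 4.3% |
| 0.8 | 0.6 | 0.6 | 0.6305 | 0.6000 | 4.8% | 2.4% |
| 0.9 | 0.5 | 0.5 | 0.7481 | 0.7368 | 1.5% | 0.8% |
| 0.9 | 0.7 | 0.65 | 0.5097 | 0.5079 | 0.4% | 0.2% |
| 0.8 | 0.6 | 0.5 | 0.6397 | 0.6389 | 0.1% | 0.1% |
| 0.9 | 0.6 | 0.55 | 0.6399 | 0.6395 | 0.1% | under 0.1% |

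Simulation with 2 million draws agrees in the cases it covered, for example 12.3% for the first row and 4.8% for the third. With equal correlations to 12 months the cut is 1.5% to 12.4%. Once the postal score predicts slightly less well than the visit score, it can fall to almost nothing.

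**On the AQLQ scale.** As an illustration, take the planning SD of 0.77 as the residual SD for 210 against 105. The 95% half-width is 1.96 × 0.77 × √(1/210 + 1/105) = 0.180. A 4.8% variance cut gives 0.180 × √0.952 = 0.176; a 12.4% cut gives 0.180 × √0.876 = 0.169.

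**The case against.** The strongest objection is that nothing here is an error. ANCOVA on one baseline score is standard, the covariate list is open-ended, and the exact set is commonly fixed in the SAP, which is not at hand. Much of this stands. A reader might infer that the protocol excludes the postal score; it does not, it only fails to name it. What remains is that the protocol itself chooses the first adjustment of its primary model and names one of two available scores. An open-ended list does not pre-specify the other.

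A second objection is that the gain cannot be shown from the documents and may be nil. That also stands. A reader might take a gain of a few per cent as assured, but the table shows cases within the assumed ranges where it is about 0.1%.

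Third, a reader might infer that the loss bites hardest on DVD versus face-to-face, with only 105 patients in one arm and a margin of 0.3. The text does not support this as it stands: the equivalence interval is not stated to be adjusted for any baseline, so a second covariate in the superiority model would leave it unchanged. Naming even one baseline score for that interval comes first.

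Fourth, the protocol does not say that the postal score enters the trial database. The form is returned before consent at the baseline visit, and identifiers are issued only at randomisation. This is a real but small data-entry and linkage cost.

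**Conclusion.** The point holds as a minor inefficiency. Two pre-randomisation scores on the primary instrument are collected and the primary ANCOVA names one. Adding the other would reduce residual variance by about 0 to 12%, about 5% at mid-range values with equal correlations to 12 months, and narrow intervals by about 0 to 6%. This rests on assumed correlations, on the postal score predicting no better than the visit score, and on truncation at 5.5 with 75% of the source population below it. It would be wrong to infer bias, an invalid primary analysis or an incorrect sample size: both scores precede randomisation, one-baseline ANCOVA is valid, and the stated superiority power reproduces without any baseline adjustment. Low priority.

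**What to change.** In section 8.1, analysis plan for superiority, name both the baseline-visit and the postal screening total AQLQ as covariates for the 12-month AQLQ analysis, with a short rule for a missing value of either.

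In the analysis plan for equivalence, state that the DVD versus face-to-face 95% interval used for the equivalence decision comes from the same ANCOVA with both scores. Without this second change the equivalence comparison gains nothing.

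The cost is entry of the postal total score in the trial database, linked to the participant identifier, and one degree of freedom. No extra visit or questionnaire is needed.
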